837 **Visit 7) Booster session will only be for intervention group.**

838

839 At visit 8 booster session the following procedures will occur:

- 840 1. Attend a 2 hour group session at the Chicago Park District or at UI  
841 Health/UIC. At the group session, participants will review successes attained  
842 and barriers, lapses, and relapses encountered.
- 843 2. Participants will be asked to complete a session evaluation form. (Appendix 9).
- 844 3. Participants will be given \$5 cash to assist with travel expenses incurred for  
845 the group visit.

846

847 An interventionist and/or [name] will attend the group session. The group will last  
848 approximately 2 hours and may be digitally recorded to assess for intervention fidelity. If  
849 a participant declines audio-recording the session, then the session will not be  
850 recorded. The PI or co-investigator may then observe a group session intermittently to  
851 assess for intervention fidelity. If the session is recorded, the PI will review portions of  
852 the session. The session will be deleted once the pilot is complete. These audio  
853 recordings will not be transcribed. Patients will receive light snacks/refreshments at the  
854 session.

855

856 **Post-maintenance data collection (all participants)**

857 The following procedures will take place at the Chicago Park District (intervention  
858 group) or Clinical Research Center at UIC (enhanced usual care):

- 859 1. Spirometry performed according to American Thoracic Society guidelines.  
860 Participants will be asked to wear nose clips and to take a deep breath in and  
861 blow their breath out as fast as they can into the spirometer. We will perform  
862 repeated measurements (3 to 8 times) to ensure accuracy of results.

- 863 2. Weight  
864 3. Incremental Shuttle Walk Test (ISWT) performed according to American  
865 Thoracic Society guidelines  
866 4. Distribution of accelerometer  
867  
868

869 The following questionnaires will be completed by REDCap survey:

- 870 1. Physical activity questionnaires  
871 2. Asthma Safety Measures  
872 3. Asthma Control Questionnaire (ACQ)  
873 4. Asthma-related quality of life questionnaire (AQLQ)  
874 5. Adult Asthma Adherence Questionnaire (AAAQ)  
875 6. PROMIS measures (Global Health, social roles satisfaction, mood, sleep)  
876 7. Active Where Questionnaire  
877 8. Self-efficacy for walking scale  
878 9. Social support for exercise survey  
879 10. Outcome expectation scale for exercise  
880 11. Sleep Apnea Scale of the Sleep Disorders Questionnaire  
881 12. Pittsburgh Sleep Quality Instrument  
882

883 This visit will last approximately 2 hours and upon completion the participant will  
884 receive \$35 cash or gift card. Patients will be offered light snacks/refreshments  
885 at this visit.  
886

887 Participants will be given a postage paid envelope and be asked to mail the  
888 accelerometer back to study team after wearing it for 1 week. Reminder  
889 calls/texts/emails will be sent if we have not received the accelerometer within 2 weeks  
890 of completion of visit 8. If needed, a central location for drop-off of the accelerometer  
891 may be arranged with the participant.  
892

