### 569 570 **3 Data Collection Visits: Baseline (week 0/Visit 1), post adoption phase (week** 571 **24/Visit 7a/b) and post maintenance phase (week 36/Visit 9) in all participants** 572 **(See appendix 8 for measures)**

573 At the data collection visits, the following procedures will take place at the Clinical  
574 Research Center at UIC or Chicago Park District location:

- 575 1. Secure informed consent (1st visit only).
- 576 2. Complete a brief demographic form.
- 577 3. Spirometry performed according to American Thoracic Society guidelines.  
578 Participants will be asked to wear nose clips and to take a deep breath in and  
579 blow their breath out as fast as they can into the spirometer. We will perform  
580 repeated measurements (3 to 8 times) to ensure accuracy of results.
- 581 4. Height and Weight
- 582 5. Incremental Shuttle Walk Test (ISWT) performed according to American  
583 Thoracic Society guidelines
- 584 6. Physical activity questionnaires

- 585 7. Asthma Safety Measures  
586 8. Asthma Control Questionnaire (ACQ)  
587 9. Asthma-related quality of life questionnaire (AQLQ)  
588 10. Adult Asthma Adherence Questionnaire (AAAQ)  
589 11. PROMIS measures (Global Health, social roles satisfaction, mood, sleep)  
590 12. Active Where Questionnaire  
591 13. Self-efficacy for walking scale  
592 14. Social support for exercise survey  
593 15. Outcome expectation scale for exercise  
594 16. Sleep Apnea Scale of the Sleep Disorders Questionnaire  
595 17. Pittsburgh Sleep Quality Instrument  
596 18. Neighborhood safety and social cohesion questionnaire  
597 19. Study randomization (1st visit only)  
598 20. Schedule asthma and physical activity (PA) education session with participant  
599 (1st visit only)  
600

601 Key research personnel will obtain consent in a private room in the Clinical  
602 Research Center. After consent is obtained, the other study procedures will be  
603 completed.  
604

605 This visit will last approximately 2 hours and upon completion the participant will  
606 receive \$35 cash or gift card. Patients will be offered light snacks/refreshments  
607 at this visit and given a visit summary sheet with their blood pressure, heart rate,  
608 weight, height, oxygen level, date of next study visit and a copy of spirometry  
609 results if desired.  
610

611 Participants will then be provided the following equipment at these data collection  
612 visits:

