613 Actigraph accelerometer: This will be given to participants to assess their baseline  
614 and post-intervention daily number of steps. Participants will be verbally instructed  
615 to wear it attached to their wrist at all times while awake. The Actigraph  
616 accelerometer (Figure 3) is a research accelerometer (1.8 inches at its largest  
617 dimension, weight 19 grams). This will be returned within 2 weeks of the data  
618 collection visit. The accelerometers can be returned either in person at the asthma  
619 and PA session, in a postage paid envelope or the participant and the research  
620 assistant will find a mutually agreeable place to pick up the accelerometer from the  
621 participant. The participant will not incur any charges if the accelerometer is lost or  
622 stolen. The data from the accelerometers will be downloaded to Actigraph software  
623 (ActiLife 6.13.3) when the accelerometers are returned. Only study ID will be used

624 in the actigraph software. No identifiable information will be maintained in the  
625 Actigraph software.

626  
627 Participants are typically asked to wear the accelerometer for 7 days (does not  
628 have to be consecutive). However, valid baseline measurement of activity can be  
629 obtained with an average of 10 hours per day for 4 days. This is the minimum  
630 amount of accelerometer data required to continue participation in the intervention.  
631 If the participant does not wear the accelerometer for sufficient time to provide valid  
632 baseline measure (ie. an average of 10 hours per day for 4 days), they will be  
633 offered a second opportunity to wear the accelerometer. If the participant declines  
634 or is unable to wear the accelerometer again within 3 weeks of returning the  
635 accelerometer, then the participant will be withdrawn from the study.

636  
637 **Enhanced Usual Care Group (home-based walking program):** The comparison  
638 group will be instructed to achieve a static goal of 10,000 steps per day. The US  
639 Surgeon General recommends accumulating 30 minutes of activity most days of the  
640 week. Assuming that an individual gets 6,000 steps from their other daily activities, 30  
641 minutes of walking can help one achieve a goal of approximately 10,000 steps per day.

642  
643 Participants will be given a Fitbit Charge HR® which will measure their daily steps (see  

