644 more detail below under visit 2). In order to attention-match for interactions with study  
645 staff, participants will attend an asthma education and physical activity training session.  
646 Newsletters with walking tips for AA women and asthma education topics will be sent  
647 twice during the intervention phases to participants in this group. Participants will come  
648 to the Clinical Research Center for data collection at weeks 24 (Visit 7b) and 36 (Visit 9)  
649 described in more detail below.

650  
651 **Asthma and physical activity (PA) education session for all participants (1-6**  
652 **weeks after baseline data collection visit)**

653 The asthma and PA education session will take place at UI Health/UIC or a Chicago  
654 Park District (CPD) location that is in close approximation to where the participants live.  
655 The exact CPD location will be determined with the help of the Chicago Park District  
656 liaison and will take into account safety of the participants and the location of where  
657 participants live. The Chicago Park District will only provide space for these visits and  
658 no Chicago Park District staff are involved in the research as recruiters or to collect  
659 data. Two separate asthma/PA education sessions will take place, one for enhanced  
660 usual care group and one for those randomized into the intervention group.

661  
662 At the asthma/PA education session the following procedures will occur:

663 1. Collection of accelerometers for those that have not already returned it.

- 664 2. Attend a 2 hour group session at the Chicago Park District or at UI  
665 Health/UIC. At the group session, participants will receive didactic asthma  
666 education and information on how to engage in physical activity with their  
667 asthma.  
668 3. Participants will be asked to complete a session evaluation form. (Appendix 9)  
669 4. Participants will be given \$5 cash to assist with travel expenses incurred for  
670 the visit.

671  
672 Key research personnel will send a reminder text, call and/or email (based on patient  
673 preference) up to 3 times the prior week to the group session stating “Asthma and  
674 physical activity session will meet at X time and X place.”  
675

676 An asthma educator, a research assistant(s) and/or [name] will attend the  
677 education session. Each education session will last approximately 2 hours. Patients will  
678 receive light snacks/refreshments at each session.  
679

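### Aim 3 baseline steps are measured after randomisation in every woman, with no stated concealment of the arm, so they can differ by arm

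*Combined protocol and SAP*

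**What the plan says.** All of this is in Section 6.0, Aim 3, unless stated otherwise.

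- **Visit 1 procedures.** In the list for the three data collection visits, item 19 is "Study randomization (1 st visit only" and item 20 is "Schedule asthma and physical activity (PA) education session with participant", also limited to the first visit.
- **Device.** After the list, the text continues "Participants will then be provided the following equipment at these data collection" visits. The device is described as "Actigraph accelerometer: This will be given to participants to assess their baseline" and post-intervention daily steps.
- **Wear.** "Participants are typically asked to wear the accelerometer for 7 days (does not" have to be consecutive); the minimum is an average of 10 hours a day for 4 days. On return: "This will be returned within 2 weeks of the data" collection visit. A woman without valid baseline wear is offered a second wear, and is withdrawn if she declines or cannot wear the device again within 3 weeks of returning it.
- **Education session.** It takes place 1 to 6 "weeks after baseline data collection visit". "Two separate asthma/PA education sessions will take place, one for enhanced" usual care and one for the intervention group. Devices not yet returned are collected there, and the Fitbit is given out there.
- **Use of baseline.** In the adoption phase, each intervention woman's step goal is capped relative to her accelerometer baseline. The comparison arm has a fixed goal of 10,000 steps a day.

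Section 11.0 says that REDCap is used to randomise and gives neither an allocation ratio nor an analysis of steps. Section 3.0 says that Aim 3 is meant to estimate efficacy so that a later trial can be powered.

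**The concern.** A baseline value protects a comparison only if allocation cannot have affected it. Steps are behaviour under the wearer's control, the trial describes no blinding, and the baseline count has a consequence in one arm only, because it anchors the individual goal there. If a woman knows her arm while she wears the device, the two arms need not walk alike that week.

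Randomisation does not protect against this, a larger sample would not remove it, and the data could not separate it from chance imbalance. At stake are the step-change estimate that a later trial may be powered on, and the individual goals of the intervention arm.

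**Working it through.** **1. Sequence.** The plan states no figure to reproduce on this point, so the check sets its passages in order.

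| Time | Event | Source |
|---|---|---|
| Visit 1 (week 0) | Randomisation; booking of the session | Data collection visits, items 19 and 20 |
| Visit 1 | ActiGraph handed out | Equipment paragraph after the list |
| Weeks 0 to 2 | About 7 days of wear, then return | Accelerometer paragraphs |
| Weeks 1 to 6 | Education session, separate by arm | Education session heading and text |

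The device is first given out at the visit where the woman is randomised, and is worn afterwards. The order of items within Visit 1 therefore does not matter: the first wear follows randomisation for every woman. Spirometry, the walk test and the questionnaires are listed ahead of item 19, so the problem is specific to accelerometer steps.

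**2. Form of the bias.** Let D be the difference in measured baseline (intervention minus comparison) caused by allocation, and Δ the true difference in steps at follow-up.

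- Change from baseline estimates Δ − D.
- A baseline-adjusted analysis estimates about Δ − βD, where β = r × SD(follow-up)/SD(baseline). With equal SDs, β = r, the baseline to follow-up correlation.
- A comparison of follow-up steps alone estimates Δ.

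**3. Illustration in steps.** The documents give neither D nor r. Assuming D = 250 to 1,000, r = 0.5 to 0.7 and equal SDs:

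| D | Bias, change score (= D) | Bias, adjusted, r = 0.5 | Bias, adjusted, r = 0.7 |
|---|---|---|---|
| 250 | 250 | 125 | 175 |
| 500 | 500 | 250 | 350 |
| 1,000 | 1,000 | 500 | 700 |

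The bias has the opposite sign to D.

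**4. Illustration as false-positive rate.** Assume 40 women per arm (80 split equally; the ratio is not stated), no true effect, a two-sided 5% test and a baseline shift of b SD. The standard errors, in SD units, are √[2(1 − r) × 2/n] for change and √[(1 − r²) × 2/n] for adjustment. The rate is Φ(−1.96 + bias/SE) + Φ(−1.96 − bias/SE).

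Example, change score with r = 0.7 and b = 0.3: SE = √(0.6 × 2/40) = 0.173, bias/SE = 1.73, rate = 41.0%.

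| r | b | Change score | Adjusted |
|---|---|---|---|
| 0.5 | 0.1 | 7.3% | 5.8% |
| 0.5 | 0.2 | 14.5% | 8.1% |
| 0.5 | 0.3 | 26.9% | 12.1% |
| 0.7 | 0.1 | 8.9% | 7.2% |
| 0.7 | 0.2 | 21.1% | 14.2% |
| 0.7 | 0.3 | 41.0% | 26.0% |

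These tables show how a shift would carry through. They do not predict that one occurs.

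**5. Room for a later randomisation.** A first wear is due back by week 2, which leaves about 4 weeks of the 1 to 6 week session window. A repeat wear is allowed within 3 weeks of return, so up to week 2 + 3 = 5, or about week 6 if the 3-week limit dates the start of a 7-day wear. For women who re-wear, little or nothing of the window is left.

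**The case against.** **Disclosure is inferred.** A reader might conclude that women are told their arm at Visit 1. The documents do not say so. Both arms' session carries the same name, the reminder wording is neutral between arms, and a date and place need not reveal an allocation. This stands. What remains is that nothing withholds the arm and that a session separate by arm is booked on the day.

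**No arm-specific content is placed in the baseline week.** The Fitbit comes at the education session and individual goals at the group sessions. The timing of the 10,000-step instruction is not stated. This stands for the first wear, where the only route that can be identified is knowledge of the arm.

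**The size is assumed.** This stands. D, r and the SDs have no source in the documents, and nothing supports a direction.

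**No analysis is named that would be biased.** Sections 9.0 and 11.0 specify no change score, adjusted model or primary steps outcome, and comparing follow-up steps alone would avoid the bias with no procedural change. This also stands, at a price in precision: relative to a valid baseline adjustment, the variance would be 1/(1 − r²) times as large, or 1.33 to 1.96 for r = 0.5 to 0.7. It would also leave the goals resting on a possibly affected baseline, and withdrawal for invalid wear after randomisation.

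**Material not seen.** The pilot procedures table (Appendix 7) and Figure 2 are not in the text supplied and might clarify when the arm is disclosed.

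**Conclusion.** The concern holds in a limited form. It is settled by the text that Aim 3 baseline steps are collected after randomisation in every woman. It is a reasonable inference, not a stated fact, that she may know her arm by then. Baseline steps can therefore differ by arm.

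If they do, a change-score comparison is biased by the full shift and a baseline-adjusted one by a fraction of it. The actual size and direction are unknown, and the figures above rest wholly on assumed shifts, correlations, equal SDs and equal arms.

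A reader might infer that baseline steps will differ, or that the efficacy estimate is already compromised. The documents support neither: they report no shift and commit to no steps analysis. Nor do they support extending the point to the other baseline measures. The case for change is that the safeguard is standard and cheap.

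**What to change.** Move items 19 and 20 out of Visit 1.

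1. Run the REDCap randomisation, and tell the woman her arm, only after a valid baseline wear (first or repeat) has been returned and downloaded.
2. Then book the education session by the telephone, text or email contact already in use.
3. For the baseline wear, keep the postal and pick-up return routes and drop return at the education session, since that session can no longer be assigned before the device is back.
4. For women who re-wear, count the session window from randomisation.
5. Align the pilot procedures table and the Visit 1 summary sheet with the new order.

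**Cost.** One extra contact per woman; session dates set about 1 to 2 weeks later, and up to about 5 weeks later for women who re-wear (6 on the longer reading of the 3-week limit); no session date on the Visit 1 summary sheet; and loss of the in-session return route.

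**Gain.** Allocation cannot influence baseline steps, and withdrawal for invalid baseline wear falls before randomisation, so it no longer removes randomised women.

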680 For missed sessions, make-up sessions will be offered (in-person or by video).  
681 Continuation in the program will be decided by the PI on a case by case basis.  
682 Participants will be strongly encouraged to make up missed sessions prior to the next  
683 scheduled group session (intervention group) or data collection visit (enhanced usual  
684 care group).  
685

686 Participants will be given the following equipment at the asthma/PA education session:  
687 1) Fitbit® physical activity monitor: Participants will be verbally instructed to wear it on  
688 their wrist at all times while awake. The Fitbit (Figure 4) is a commercially-available  
689 physical activity monitor (0.83 inches wide, weight 0.8 ounces). The wristbands are  
690 adjustable and data from our focus groups revealed that participants would prefer a  
691 wrist-based than a waist-based physical activity monitor. Participants will be asked to  
692 download the fitbit app to their smartphone or tablet and asked to create an account.  
693 Participants will be referred to the Fitbit website for troubleshooting. This will allow for  
694 physical activity data transmission to the Fitbit study database which will not contain any  
695 identifiable information. If a participant is unable to or does not want to download the  
696 fitbit app then they will write their daily steps into a journal which they will bring to each  
697 study visit. Participants will not be responsible for the cost of the Fitbit if it is lost or  
698 stolen.  
699

700 Daily physical activity, heart rate and status of the Fitbit (e.g., battery) will be monitored  
701 in real time using a Fitbit study database. Only physical activity data (i.e., step counts,  
702 time worn using heart rate, minutes active, distance walked) of the participant will be  
703 kept in the Fitbit study database. This is necessary for recording of detailed physical

704 activity data as the pedometers have limited data storage capacity. Only study ID will be  
705 used in the Fitbit study database. No identifiable information will be maintained in the  
706 Fitbit database.

707  
708 **Group sessions (Intervention group only):** Women randomized into the intervention  
709 group will also attend group sessions in 2 phases: Adoption and Maintenance (See  
710 Figure 2).

711  
712 **Adoption phase (5 sessions every 4 weeks)**

713 The group session will take place at UI Health/UIC or a Chicago Park District (CPD)  

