714 location that is in close approximation to where the participants live. The exact CPD  
715 location will be determined with the help of the Chicago Park District liaison and will take  
716 into account safety of the participants and the location of where participants live. The  
717 Chicago Park District will only provide space for these visits and no Chicago Park  
718 District staff are involved in the research as recruiters, interventionists, asthma  
719 educators or to collect data.

720  
721 At each group session the following will occur:

- 722 1. Women will attend a 2 hour group session at the Chicago Park District or at  
723 UI Health/UIC. At the group session, participants will continue to receive  
724 asthma education (short videos and/or didactic session), watch a video on  
725 how to get started to walk and what barriers they may face. Participants will  
726 be asked to share their experiences engaging in physical activity with asthma.
- 727 2. Participant will be given an individualized step-goal not to exceed 3000 steps  
728 above their baseline calculated from accelerometer data over the entire  
729 course of the study.
- 730 3. Each participant will be given an ACTION participant manual (1st group  
731 session only).
- 732 4. Participants will be encouraged to walk during the group session for up to 15  
733 minutes. The interventionist and Chicago Park District liaison will identify safe  
734 locations for the women to walk at the group session site. Women will be able  
735 to walk at their own pace and stop at anytime. If the participant does not want  
736 to participate in the walking portion of the group visit they may opt-out by  
737 verbally telling the interventionist that they do not want to participate.
- 738 5. Participants will be asked to complete a session evaluation form. (Appendix  
739 9).
- 740 6. Participants will be given \$5 cash to assist with travel expenses incurred for  
741 each group visit.

742

743 At the last group session in the adoptive phase, the following procedures will occur and  
744 the participant will receive \$35 cash or gift card for this visit only:

745 :

- 746 1. Spirometry performed according to American Thoracic Society guidelines.  
747 Participants will be asked to wear nose clips and to take a deep breath in and  
748 blow their breath out as fast as they can into the spirometer. We will perform  

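### The repeat baseline accelerometer wear may follow the education session and Fitbit hand-out, so for some re-wearers baseline steps are not pre-programme

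*Combined protocol and SAP*

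**What the plan says.** All references are to Section 6.0, Aim 3 (Pilot), unless stated.

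- **Purpose.** Under the data collection visits: "Actigraph accelerometer: This will be given to participants to assess their baseline" and post-intervention daily steps.
- **Return.** The device is due back within 2 weeks of the visit ("dimension, weight 19 grams). This will be returned within 2 weeks of the data" collection visit). One permitted route is the education session ("collection visit. The accelerometers can be returned either in person at the asthma" and PA session). The others are a prepaid envelope or an agreed pick-up.
- **Reading of wear.** Data are downloaded to the software ("ActiLife 6.13.3) when the accelerometers are returned. Only study ID will be used").
- **Minimum wear and re-wear.** An average of 10 hours a day for 4 days is needed to stay in the intervention. A woman who falls short is "offered a second opportunity to wear the accelerometer. If the participant declines" or cannot re-wear within 3 weeks of returning it, she is withdrawn.
- **Education session.** It takes place 1-6 weeks after the baseline visit, for all participants, with separate sessions by arm. Its first listed procedure is "Collection of accelerometers for those that have not already returned it". Its second is the 2-hour group session, which covers how to be active with asthma.
- **Fitbit.** "Participants will be given the following equipment at the asthma/PA education session", and the item listed is the Fitbit.
- **Goal ceiling.** In the adoption phase, the intervention arm's individual step goal may not exceed 3,000 steps "above their baseline calculated from accelerometer data over the entire" course of the study.
- **Randomization.** It is a Visit 1 procedure, so all baseline wear comes after allocation.

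**The concern.** A baseline step count should describe activity before the programme starts. The plan allows some second attempts at that measurement to be made after a woman has been taught how to be active with asthma and has been given an activity monitor to wear on her wrist.

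Two quantities depend on the value. The first is her change in steps, which is too small if activity has already risen. Aim 3 is meant to estimate efficacy so that a later trial can be powered, so an understated gain could carry over into that design. The second is the ceiling on her individual goal in the intervention arm, which stays tied to the baseline throughout the study.

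The women affected are not a random subset. They are those who had difficulty with the first wear. Because the arms attend separate sessions after randomization, a baseline taken after the session could also be affected by allocation, which weakens it both as a reference for change and as an adjustment covariate.

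**Working it through.** The plan gives no figure to reproduce: Section 11.0 states that no sample size calculation was made for Aim 3. The check is one of dates, in days from Visit 1, followed by simple bias arithmetic.

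**Inputs from the protocol**
- First return: day 14 at the latest under the 2-week rule. Day 7 is taken as the earliest, because 7 days of wear are usually requested.
- Education session: day 7 to day 42 (1-6 weeks).
- Re-wear: within 21 days of return.
- Group sessions: five, every 4 weeks, the last at week 24.

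**Route 1: device returned at the session.** Too little wear is seen only after download, which follows the return. Education and the Fitbit are delivered at that same session. The re-wear therefore normally comes after both.

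**Route 2: device returned by day 14 by another route.** The latest end of re-wear is 14 + 21 = day 35. The session may be held from day 7, so the windows overlap. For example, a return on day 14, a session on day 21 and a re-wear on days 22-28 meet every stated rule.

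To gauge the overlap, give equal weight to all permitted dates (an assumption). Let the return fall on days 7-14 (mean 10.5) and the session on one of 36 days (7-42), with the re-wear finished within 21 days of return.
- 7-day re-wear: mean start day 10.5 + 8 = 18.5. Wholly after the session: (18.5 - 6)/36 = 35%. Straddling it: 6/36 = 17%.
- 4-day re-wear: mean start day 10.5 + 9.5 = 20. Wholly after: (20 - 6)/36 = 39%. Straddling: 3/36 = 8%.

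Some of these combinations place the session before the return, when the device should have been collected there. Without them there are 260 return-session pairs (36 + 35 + ... + 29). The share wholly after becomes 8 x 9/260 = 28% (7-day) or 8 x 10.5/260 = 32% (4-day). The share straddling becomes 48/260 = 18% or 24/260 = 9%. On either count the overlap is not a rare corner case among re-wearers.

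**Late return.** A device collected at a day-42 session could be re-worn to 42 + 21 = day 63 (week 9). Counting back, the first group session is at 24 - 4 x 4 = week 8. This path needs a return four weeks past the 2-week limit.

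**Size (rise u and share affected p are assumptions)**
- Affected woman: change understated by u. Her ceiling lies 3,000 + u above her pre-programme level.

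| u (steps/day) | Ceiling above pre-programme level | u / 3,000 |
|---|---|---|
| 500 | 3,500 | 17% |
| 1,000 | 4,000 | 33% |
| 2,000 | 5,000 | 67% |

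- Arm mean change understated by p x u: from 0.05 x 500 = 25 to 0.25 x 2,000 = 500 steps/day.
- Between arms: 0 if p and u are equal in both arms; up to p x u, in either direction, if only one arm is affected.

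**Feasibility of ordering the steps.** A return on day 14 plus 21 days ends on day 35, before day 42. If the 3-week limit means only that re-wear must start by then, a 7-day wear ends on 14 + 21 + 6 = day 41, still inside the window but with one day to spare.

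**The case against.** The best reply is that the plan already has a gate, since valid wear is a condition of continuing in the intervention. But that condition does not hold back the education session or the Fitbit. The session's own procedure list expects some devices to be collected there, before anyone can know whether wear was sufficient.

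A second reply is that the order may be fixed elsewhere. Figure 2 and the pilot table of study procedures (Appendix 7b) are not in the supplied text, so the finding is that no available section sets the order. This limit stands.

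Several stronger readings are tempting but not supported:
- *That re-wear commonly follows the first group session.* This requires a late return against the 2-week rule. An on-time return ends re-wear by week 5 if it must be finished within 3 weeks.
- *That comparison-arm re-wear takes place under the 10,000-step instruction.* The protocol does not say when that instruction is given. If it is given at Visit 1, first wears are affected too.
- *That the efficacy estimate is biased in a known direction.* No analysis of steps is specified for Aim 3; its use is inferred from the device's stated purpose. Both arms get a session and a Fitbit, so between-arm bias may partly cancel.
- *That every affected woman's goal rises.* The 3,000-step figure is a ceiling, so a goal changes only where the ceiling binds.

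**Conclusion.** The point holds as a sequencing gap. For women who return the device at the session and need a second wear, the repeat baseline will normally follow education and the Fitbit. For women who return it by day 14, it can. Those whose re-wear is finished before the session are unaffected.

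If activity rises after the session, the direction is clear within person and within arm: change is understated. In the intervention arm, the goal ceiling is also anchored too high relative to pre-programme activity. The size is unknown. The range of 25-500 steps/day for an arm's mean change rests entirely on an assumed 5-25% affected and an assumed rise of 500-2,000 steps/day, and it is not a between-arm bias. That bias may be zero or of either sign. The gap merits correction because it follows from the plan's own return and re-wear rules and can be closed within the existing windows.

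**What to change.** In the Aim 3 accelerometer text, require the baseline device to be returned and downloaded, and any re-wear completed, before the woman attends the education session and receives the Fitbit. Then:
- remove the session as a return route for the baseline device, and amend the session's collection step to match;
- reconcile the 2-week return rule with collection at a session as late as week 6;
- say whether the 3-week limit applies to the start or the end of re-wear;
- check that Figure 2 and Appendix 7b show the same order.

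Where a re-wear after the session cannot be avoided, record its date relative to the session, flag it, and report the step-change estimate with and without those women. Setting their baseline to missing by default is not advised: it would discard data selectively from women with wear difficulty, in a pilot of at most 80.

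The cost is small but not nil. The edits touch the return, session and Fitbit text. The session date booked at Visit 1 becomes provisional until wear is confirmed. A few women would attend a later or make-up session, and make-up sessions are already offered for missed ones.
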